Submitted in NIH grant renewal application 3/2/2015
Implemented upon funding 2/24/2016

15. Data analysis

15a. Descriptive analyses. We will describe creation of the VITAL diabetes sub-cohort according to CONSORT guidelines, including numbers of participants who consent to VITAL participation; report a diagnosis of diabetes; are approached for the DKD ancillary study; enroll in the DKD ancillary study; and complete year 2 and 5 year biosample collections. We will document reasons that participants do not complete the proposed studies. Among participants recruited into the DKD ancillary study, we will compare baseline characteristics of those who do and do not return at least one follow-up biosample collection. Among participants who return a follow-up biospecimen, we will describe by treatment assignment baseline characteristics and changes in clinical characteristics over the course of the study.

15b. Study outcomes. With an extension of follow-up from 2 to 5 years, we will have sufficient time to effectively evaluate change in estimated GFR (eGFR), a clinically relevant outcome.¹⁷⁵⁻¹⁷⁹ Therefore, if this competitive renewal is funded, change in eGFR from baseline to year 5 will supplant 2-year changes in albuminuria and eGFR as our primary study outcome. Change in eGFR will be calculated and summarized by treatment group as $[eGFR_5 - eGFR_0]$, where $eGFR_5$ represents eGFR at follow-up (year 5) and $eGFR_0$ represents eGFR at baseline. As secondary outcomes, we will examine changes in urine ACR from baseline to years 2 and 5, time to the development of rapid eGFR loss (loss of eGFR $\geq 40\%$ from baseline to year 2 or 5),¹⁷⁵⁻¹⁷⁹ and time to a composite of rapid eGFR loss, end stage renal disease (maintenance dialysis or kidney transplant verified by medical records review), or death. The composite outcome addresses large changes in eGFR which have particularly high clinical importance and reduces the potential impact of competing risks that preclude assessment of eGFR at follow-up.

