15c. Intention to treat and missing data. Analyses will be performed in accordance with the intent-to-treat principle, meaning that all participants who return at least one follow-up biosample will be included in analyses, regardless of adherence or other characteristics observed after randomization. Multiple imputation for study participants missing year 5 eGFR will be conducted using chained equations, utilizing baseline data as well as eGFR and urine ACR data available at year 2.¹⁸⁰ Results from 10 imputation datasets will be combined using Rubin's rules.¹⁸¹

15d. Treatment interaction. We will assess for interaction of the study interventions (vitamin D and omega-3 fatty acids) for the primary outcome.¹⁸² We will use a linear mixed model to test for interaction:¹⁸³

$$\text{Equation 1: } eGFR_{ij} = \beta_0 + \beta_1(\text{vitamin D}_i) + \beta_2(\omega-3 \text{ FA}_i) + \beta_3(\text{vitamin D}_i \times \omega-3 \text{ FA}_i) + \beta_4(\text{vitamin D}_i \times t_{ij}) + \beta_5(\omega-3 \text{ FA}_i \times t_{ij}) + \beta_6(\text{vitamin D}_i \times \omega-3 \text{ FA}_i \times t_{ij}) + a_i + e_{ij}$$

where i denotes the i th participant and $j=0,2,5$ represents the time period, t is time modeled categorically, (vitamin D) is active vitamin D treatment assignment (yes/no), (ω -3 FA) is active omega-3 treatment assignment (yes/no), a_i is a random effect for patient, and e is statistical error. A p value < 0.05 for β_6 will be interpreted as evidence of interaction. If we observe interaction, all analyses will separately compare each of the 3 active treatment groups to the treatment group which receives (placebo + placebo). If there is no evidence of interaction, as hypothesized, all participants assigned to any active vitamin D will be compared to all participants assigned to placebo vitamin D, and all participants assigned to any active omega-3 fatty acids will be compared to all participants assigned to placebo omega-3 fatty acids.

15e. Hypothesis testing. The primary outcome is a continuous variable which will be tested using a linear mixed model with random intercepts. To test whether the change in eGFR differs by vitamin D treatment assignment in the absence of interaction with omega-3 fatty acids, we will test:

$$\text{Equation 2: } eGFR_{ij} = \beta_0 + \beta_1(\text{vitamin D}_i) + \beta_2(t_{ij}) + \beta_3(\text{vitamin D}_i \times t_{ij}) + a_i + e_{ij}$$

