where β_3 represents the difference in change in eGFR over time, comparing those on active vitamin D₃ to those on placebo. The corresponding 95% confidence interval and p-value reflect statistical significance of the treatment effect. We will use this model to describe treatment effects at years 2 and 5 but reserve statistical inference for year 5 alone. Corresponding equations will test the effect of omega-3 treatment assignment on eGFR as well as treatment effects on urine ACR, analyzed as a log-transformed continuous variable. The relatively large sample size makes it likely that few or no substantial differences in baseline characteristics will be present. In the event that any baseline characteristics are not balanced between treatment groups, sensitivity analyses will add to the model additional terms for such baseline characteristics. If we observe differences by treatment group in medication use (e.g. glucose-lowering or antihypertensive medications) or

laboratory covariates (e.g. hemoglobin A1c, CRP, IL-6) over follow-up, we will explore whether such differences may mediate or attenuate treatment effects by adding terms for these covariates to the model. We will assess secondary categorical outcomes using discrete Cox proportional hazards models.¹⁸⁴

15f. Subgroup analyses. For the vitamin D intervention, prespecified subgroup analyses will be based on baseline total and bioavailable serum 25(OH)D concentrations, urine ACR, and eGFR as well as race/ethnicity: we hypothesize that effects will be greater among participants who have low 25(OH)D at baseline, who have DKD (urine ACR ≥ 30 mg/g or eGFR < 60 mL/min/m 2) at baseline, or are Caucasian.^{185,186} For the omega-3 fatty acid intervention, prespecified subgroup analyses will be based on baseline levels of EPA+DHA and hsCRP: we hypothesize that effects will be greater among participants who low levels of EPA+DHA or high concentrations of hsCRP at baseline. Effect modification will be tested by including interaction terms of treatment assignment with subgroup in linear mixed models (Equation 2).

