15g. Exploratory adherence and efficacy analyses. All primary analyses will be performed according to the intent-to-treat principle (Section D15e). We plan secondary, *exploratory* analyses for the following limited purposes: (a) to evaluate whether null findings, if observed, are robust (i.e. not readily attributable to defects in the study interventions or their administration); and/or (b) to more comprehensively evaluate the potential range of treatment effects, if treatment effects are observed. We understand and acknowledge that these analyses, which are based on data collected after randomization, may introduce bias into study results. We will therefore use caution to limit their interpretation. We will first repeat analyses among the subset of participants who report continuous adherence to $\geq 80\%$ of study medications. In addition, we will assess whether changes in 25(OH)D and EPA+DHA levels are associated with changes in urine ACR and eGFR. For the latter analyses, change in 25(OH)D concentrations or change in EPA+DHA concentration (continuous variables) will replace treatment assignment in linear mixed models.

D16. Power. We calculated power using simulation (2000 replications) and the following assumptions: independent and equal allocation of participants to each treatment; 1,058 participants (80%) contributing at least one follow-up blood sample (as supported in Section D10); variation in eGFR and its change over time as observed in the preliminary data from our study population (Section D12); and no interaction between treatments. With these assumptions, we have 80% power (two-sided alpha=0.05) to detect a 2.3 mL/min/1.73m 2 difference in eGFR at year 5, comparing each active treatment to placebo. Power for alternative effect sizes is shown in Figure 7. We do not present power for secondary outcomes because the incidence of these outcomes is difficult to predict with available data.

[figure not shown]

Figure 7. Study power by effect size for the primary outcome (difference in estimated GFR in mL/min/1.73m 2).

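### Ten imputations give valid primary inference but leave avoidable seed-to-seed noise in the year-5 p-value; a larger number is a nearly free, minor improvement

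*Combined protocol and SAP*

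**What the plan says.** The Protocol Addendum makes year 5 the primary time point: "change in eGFR from baseline to year 5 will supplant 2-year changes in albuminuria and eGFR as our primary study outcome" (15b). Section 15e describes effects at years 2 and 5 but will "reserve statistical inference for year 5 alone". The analysis set in 15c is set by follow-up returns: "all participants who return at least one follow-up biosample will be included in analyses". Some of that set will have year 2 but not year 5, and for them "Multiple imputation for study participants missing year 5 eGFR will be conducted using chained equations", with baseline data and year-2 eGFR and ACR as predictors. Then "Results from 10 imputation datasets will be combined using" Rubin's rules.

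Section D16 gives the scale: "1,058 participants (80%) contributing at least one follow-up blood sample", "independent and equal allocation of participants to each treatment", and "we have 80% power (two-sided alpha=0.05) to detect a 2.3 mL/min/1.73m"² difference at year 5.

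The supplied text states no random seed, no limit on Monte Carlo error, no rule tying the number of imputations to the amount of missing data, and no expected share of the 1,058 without year 5.

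**The concern.** Multiple imputation draws random values, so the pooled estimate, interval and p-value vary with the seed. The variation shrinks as the number of imputations m grows. Here the imputed visit is the one that carries the primary test, and that test is read against 0.05 for each of two agents. With m = 10, two correct executions of the plan on the same data could fall on opposite sides of 0.05 if the result is borderline.

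The interaction test in 15d may be exposed too. A p-value below 0.05 there switches all analyses from the factorial margins to three separate comparisons with double placebo. The plan does not say whether that test is run on imputed data.

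**Working it through.** **The plan's own figure.** D16 cannot be reproduced independently, because its eGFR variability is in a Section D12 that is not among the supplied documents. Solving backwards from 80% power, the standard error (SE) is 2.3 / (1.960 + 0.842) = 0.821. With 529 per arm, the SD of change is 0.821 × √(529/2) = 13.35. As a plausibility check, the original plan (VI.h) has SD 25 and correlation 0.834. Its residual SD is 25 × √(1 − 0.834²) = 13.79, which gives 77.4% power for 2.3. With 600 per arm it gives 90.4% for 2.6, matching the 90% in Table 2. The SD is used below only to convert to mL/min/1.73m²; the p-value results do not depend on it.

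**Assumptions not in the documents.** A share π = 10%, 20% or 30% of the analysed set lacks year-5 eGFR, completely at random. Correlation between any two visits is ρ = 0.8. Imputation uses baseline and year-2 eGFR.

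**Fraction of missing information (FMI).** In units of the eGFR variance, the change from baseline has variance 2(1 − ρ) = 0.40. The residual variance of year 5 given baseline and year 2 is r = 1 − 2ρ²/(1 + ρ) = 0.289. Then FMI = rπ/(1−π) / [0.40 + rπ/(1−π)]:
- 10% missing: 0.032 / 0.432 = 0.07
- 20% missing: 0.072 / 0.472 = 0.15
- 30% missing: 0.124 / 0.524 = 0.24

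**Seed-to-seed noise.** The SD of the pooled z over seeds is s = √(FMI/m). The 95% range of p for data with seed-free z = 2.0 (p = 0.0455) comes from 2.0 ± 1.96s.

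| FMI | s, m=10 | × 0.821 (mL/min/1.73m²) | p range, m=10 | p range, m=100 |
|---|---|---|---|---|
| 0.07 | 0.084 | 0.07 | 0.030–0.066 | 0.040–0.051 |
| 0.15 | 0.122 | 0.10 | 0.025–0.078 | 0.038–0.054 |
| 0.24 | 0.155 | 0.13 | 0.021–0.090 | 0.036–0.057 |

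**How often it matters over all trials.** Let the seed-free Z be N(μ, 1), with μ = 0 (no effect) or 2.80 (80% power). For a given Z, let q be the probability over seeds that |Z + sε| > 1.96, where ε is standard normal. Two seeds disagree with probability 2q(1 − q), averaged over Z.

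| FMI | no effect, m=10 | no effect, m=100 | 80% power, m=10 | 80% power, m=100 |
|---|---|---|---|---|
| 0.07 | 1.1% | 0.35% | 2.6% | 0.84% |
| 0.15 | 1.6% | 0.51% | 3.9% | 1.22% |
| 0.24 | 2.1% | 0.65% | 4.9% | 1.55% |

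These figures are per agent.

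**Power cost.** Rubin's variance at finite m exceeds its limit by the factor 1 + FMI/m. At m = 10 the SE rises by √(1 + FMI/10) − 1 = 0.35%, 0.75% and 1.2%. Power falls from 80% to 79.7%, 79.4% and 79.1%.

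**Simulation check.** One dataset was fixed per setting (N = 1,058, SD of change 13.35, correlation 0.8) and re-imputed with 1,000 seeds at m = 10 and 400 at m = 100. The data were set to a seed-free p of 0.04.

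| Missing | 95% range of p, m=10 | Seeds above 0.05, m=10 | 95% range of p, m=100 | Seeds above 0.05, m=100 |
|---|---|---|---|---|
| 10% | 0.026–0.063 | 17% | 0.035–0.046 | 0% |
| 20% | 0.022–0.083 | 34% | 0.034–0.050 | 3.5% |
| 30% | 0.017–0.101 | 35% | 0.030–0.052 | 4% |

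At 5% missing and m = 10, the range was 0.031–0.054, with 7% of seeds above 0.05.

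**The case against.** The strongest reply is that nothing here is an error. Rubin's rules carry the (1 + 1/m) term, so the interval already allows for the finite number of imputations. A reader might infer that ten imputations bias the estimate or inflate type I error. They do neither, and that part of the reply stands in full.

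A reader might also infer from the p-value ranges that the trial's conclusion generally hangs on the seed. Those ranges start from data already next to 0.05. Over all trials, about 95–99% would keep their verdict for a given agent, and results well away from 0.05 do not change.

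The size also rests on assumptions. The missing share is not stated, and D16 points to Sections D10 and D12, which are not supplied. The correlation of 0.8 is assumed; the only documented value near it, 0.834, belongs to the superseded power calculation and another cohort. The back-calculated SD treats all 1,058 as having year 5, although D16 counts people with at least one follow-up blood sample, and its simulated power may already allow for missing visits. The plan also imputes from other baseline data and year-2 ACR, which could lower the missing information. Nor can one say that there was no reason for 10: the references cited for the imputation are not in the supplied list, which ends at 160.

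Finally, the m = 100 ranges at z = 2.0 still cross 0.05, so no particular number is uniquely right. What survives is narrower: the noise is real, it falls on the primary test, and it can be made much smaller at almost no cost.

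**Conclusion.** The point holds as a minor, free improvement in the reproducibility and precision of the primary result. It is not a flaw in validity. Under the assumed FMI of 7–24%, moving from 10 to 100 imputations cuts the chance that two seeds disagree at 0.05 from about 1–2% to 0.35–0.65% with no effect, and from about 3–5% to 0.84–1.55% at the 80%-power effect. The power recovered is under 1 percentage point. If only about 5% lack year 5, the gain is smaller still. If the missing share exceeds 30% or the visits correlate less well, it is larger.

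**What to change.** In 15c, replace 10 with a larger number of imputations (100, for example). Record the seed before the analysis, and report the Monte Carlo error of the primary estimate and p-value. State in 15d whether the interaction test uses the imputed data and, if so, use the same number there. The seed makes the run auditable; the larger number makes the answer more stable. Neither removes the dependence entirely, so the reported Monte Carlo error is what tells a reader whether a borderline p-value is settled.

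The cost is one changed number, two or three sentences, and a little computing for one continuous outcome in about 1,058 people. The estimand, the data collected and the sample size stay the same.

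### The vitamin D by omega-3 interaction model (Addendum 15d, Equation 1) has no time main effect, so its β6 test absorbs the eGFR decline common to all arms and can wrongly end the factorial analysis

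*Combined protocol and SAP*

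**What the plan says.** Protocol Addendum, section 15d, sets out a linear mixed model for eGFR at years 0, 2 and 5. Equation 1 contains, in order:

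- an intercept (β0);
- vitamin D, omega-3 and their product (β1 to β3);
- each of those three multiplied by time (β4 to β6);
- a random participant effect and error.

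The coefficients are numbered without a gap, and time never stands alone. Each treatment is a yes/no indicator. For time, the text says that j "represents the time period, t is time modeled categorically".

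The decision rule is "A p value < 0.05 for β_6 will be interpreted as evidence of interaction". The consequence is "If we observe interaction, all analyses will separately compare each of the 3 active treatment groups" with the double-placebo group. Without evidence of interaction, each agent is compared at its factorial margin.

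Equation 2 in section 15e, the model for the treatment effect itself, does include time as a separate term (β2). No other section adds such a term to Equation 1.

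**The concern.** A three-way product is interpretable as an interaction only when all its lower-order terms are in the model. Here the time main effect is missing. The reference cell (placebo + placebo) is described by the intercept alone, so the model allows it no change over five years. The other three cells are free at every visit. Whatever change all arms share is therefore loaded onto the treatment-by-time terms, including β6.

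This matters because β6 acts as a gate. A p-value below 0.05 changes the primary comparison for both agents, roughly halves the numbers in each comparison, and would be reported as a drug interaction. The error can also hide a real effect: an antagonistic interaction equal in size to the shared decline would be cancelled.

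**Working it through.** **1. What β6 estimates.** Write the fitted mean change from baseline to year 5 in each cell under Equation 1 with 0/1 indicators:

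- placebo + placebo: 0 (forced)
- vitamin D only: β4
- omega-3 only: β5
- both: β4 + β5 + β6

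So β6 = change(both) − change(D only) − change(omega-3 only). The proper interaction contrast also adds change(placebo + placebo). Hence β6 as written = true interaction − change(placebo + placebo). If neither agent has an effect and every cell changes by −d, β6 = −d + d + d = d.

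A parameter count agrees. Four cells at three visits have 12 means. Equation 1 with categorical time has 4 + 6 = 10 fixed effects. Adding two visit indicators gives 12.

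**2. Inputs.**

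- Sample size, Addendum D16: "1,058 participants (80%) contributing at least one follow-up blood sample", equally allocated, so 1,058/4 = 264.5 per cell and 529 per margin.
- eGFR variation, section VI.h: SD 25, correlation with baseline 0.834.
- Shared decline: not stated in the documents, so taken as an assumption over 0 to 10 mL/min/1.73m² at year 5.

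**3. Reproducing the plan's own power first.** The ANCOVA SD is 25 × √(1 − 0.834²) = 13.79. With 600 v 600 and a difference of 2.6, power is 90.4%, against the stated 90% in VI.h. The SD and correlation are therefore usable. The SD of change is 25 × √(2 × (1 − 0.834)) = 14.40.

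The addendum bases its own power on preliminary data not shown in the documents. Its 80% for 2.3 with 529 v 529 implies an SD of 2.3 / (2.80 × √(2/529)) = 13.35. The rates below are given for both SDs.

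**4. False-trigger rate.** β6 as written combines three independent cell changes, so SE = SD × √(3/264.5):

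- SD 14.40: SE = 1.53
- SD 13.35: SE = 1.42

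The probability of p < 0.05 is P(|Z + d/SE| > 1.96). A simulation checked this: 2,000 trials per scenario, a random-intercept model fitted by REML, complete data at years 0, 2 and 5, SD 25, correlation 0.834, no treatment effect, no interaction, and the same linear decline in all arms.

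| Shared decline at year 5 | Formula, SD 14.40 | Formula, SD 13.35 | Simulated, year-5 β6 as written | Simulated, joint test of both β6 terms | Simulated, year-5 β6 with time added |
|---|---|---|---|---|---|
| 0 | 5% | 5% | 6.3% | 5.1% | 4.8% |
| 1 | 10% | 11% | 8.6% | 7.2% | 4.0% |
| 2 | 26% | 29% | 25% | 19% | 5.4% |
| 3 | 50% | 56% | 50% | 42% | 5.6% |
| 5 | 90% | 94% | 90% | 84% | 5.3% |
| 7.5 | 99.8% | >99% | 99.7% | 99.6% | 5.2% |
| 10 | >99% | >99% | 100% | 100% | 5.1% |

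The mean simulated β6 as written was 1.00, 2.01, 2.99, 5.02, 7.49 and 10.05 for declines of 1 to 10. With time added it stayed close to 0 throughout.

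**5. Cost of a false trigger.** At the margins, 80% power corresponds to a standardised effect of 2.80. Halving each group divides this by √2, giving 1.98. Power is then P(Z > 1.96 − 1.98) = 51% for each single-cell comparison.

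**The case against.** The strongest reply is that this is a drafting slip. Equation 2 has the time term. The interaction model in the original protocol (VI.d) needed none, because an ANCOVA intercept absorbs any shared change. Nothing suggests that the authors meant to hold the double-placebo arm flat. Some formula-based software, given the treatments as factors, would also restore the missing term and produce a valid test. Both points are fair, but the equation as written does not contain the term, and the primary comparison should not depend on how an analyst codes two indicators.

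A second reply concerns size. No mean eGFR change is given, and the documents' hints conflict. VI.h calls differences such as 2.6 mL/min/1.73m² modest beside the changes seen in comparable cohorts. A shared decline of only 2.6 already gives a false-trigger rate of about 40% (SE 1.53). Against that, VI.h expects about 17% to lose at least 12 mL/min over four years. With SD 14.40 and normality, that implies a mean change of −12 + 0.954 × 14.40 = +1.7, and a rate near 21%. Missing year-5 values would also widen the SE and lower the rates. So the percentages are conditional illustrations. The bias is absent only if the shared change is zero, and it operates in either direction.

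Third, Equation 2 is correctly specified. After a false trigger each active arm is still compared with its randomised control, so the missing term does not itself bias the treatment estimates. That stands. The damage is a wrong switch of the primary comparison, lost power and a spurious interaction claim.

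**Conclusion.** The concern holds. As prespecified, the year-5 β6 equals the true interaction minus the change in the placebo + placebo cell, so the test does not have its nominal 5% error whenever mean eGFR changes over time. That result is algebra and needs no variance assumption. It rests only on the literal reading of Equation 1, with 0/1 treatment indicators.

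The size depends on the unknown shared decline. For declines of 2.5, 5 and 7.5 over five years (assumed 0.5 to 1.5 mL/min/1.73m² per year), the formula with SE 1.53 gives false-trigger rates of 37%, 90% and 99.8%. At a decline of 1 the rate is about 10%. These figures assume the original protocol's eGFR variation and complete year-5 data on 1,058 participants. This should be corrected before analysis, because a stated rule acts on this p-value.

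**What to change.** Add the main effect of time to Equation 1 as indicators for years 2 and 5, matching Equation 2. Because time is categorical, β6 is two coefficients. State that the interaction decision uses the year-5 coefficient of vitamin D × omega-3 × time, consistent with section 15e, which limits inference to year 5.

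In the simulation this brought the false-positive rate to between 4.0% and 5.6% at every shared decline from 0 to 10. The corrected contrast has a larger standard error (SD × √(4/264.5) = 1.77 rather than 1.53 with SD 14.40), which is the true precision of a four-cell interaction. The cost is one term in one equation and one sentence, with no effect on data collection or sample size.

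### Letting the interaction p-value choose the primary contrast raises each agent's error rate from 5.0% to about 6.4%, and a chance flag halves the comparison

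*Combined protocol and SAP*

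**What the plan says.** Addendum section 15d tests the three-way term (vitamin D × omega-3 × time) in a linear mixed model for eGFR: "A p value < 0.05 for β_6 will be interpreted as evidence of interaction". If that happens, "If we observe interaction, all analyses will separately compare each of the 3 active treatment groups" with the double-placebo group. If it does not, "all participants assigned to any active vitamin D will be compared to all participants assigned to placebo vitamin D", and omega-3 is handled in the same way. The interaction is tested for the primary outcome only, but the consequence is worded for all analyses.

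Section 15e takes the resulting 95% interval and p-value at face value. Section D16 says "we have 80% power (two-sided alpha=0.05) to detect a 2.3 mL/min/1.73m 2 difference in eGFR at year 5", and lists among its assumptions "and no interaction between treatments". It gives no power for the comparisons that follow a switch.

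The main protocol had a similar rule (VI.d). It set alpha at 0.05 with no multiplicity adjustment (VI.e), and in VI.h it disclosed the cost of switching: 80% power for 3.2 mL/min/1.73m² in eGFR or 20% in urine ACR.

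**The concern.** The same data first select the contrast and then test it. That would be harmless if the selecting statistic were independent of every contrast it might select. It is independent of the marginal contrasts, but not of the two single-agent contrasts. Both of those use the double-placebo cell and one single-agent cell, and both cells also enter the interaction. A switch therefore tends to occur in trials where a single-agent contrast is extreme by chance.

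Two things are at stake. The reported p-values and 95% intervals would not have their nominal properties. A chance interaction would also replace a half-versus-half comparison with quarter-versus-quarter comparisons, for secondary outcomes as well as eGFR.

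**Working it through.** **Inputs.** Equal allocation to four cells (main protocol IV.c: blocks of eight, two per combination). Interaction test at 0.05 and the switching rule (Addendum 15d). Final tests two-sided at 0.05, 1,058 analysed, 80% power at 2.3 (D16). For the main protocol (VI.h): 1,200 analysed; eGFR SD 25 and correlation 0.834; log ACR SD 1.59 and correlation 0.78. Assumed: independent, normal cell estimates with equal variance, and a 5% flag rate when there is no interaction.

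**1. The plan's own figures.** Residual SD = SD × √(1 − r²): eGFR 25 × √(1 − 0.834²) = 13.79; log ACR 1.59 × √(1 − 0.78²) = 0.995. Power = Φ(δ / (SD × √(2/n)) − 1.96).
- Factorial, 600 vs 600, eGFR 2.6: 2.6 / 0.796 = 3.27, power 90.4% (stated 90%).
- Switched, 300 vs 300, eGFR 3.2: 3.2 / 1.126 = 2.84, power 81.1% (stated 80%).
- Switched, ACR 20% lower: 0.223 / 0.0812 = 2.75, power 78.4% (stated 80%).

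These agree within two points. The D16 figure came from simulation with an SD the documents do not give, so it cannot be checked independently. It implies an SD of 2.3 / (2.80 × √(2/529)) = 13.35; with 13.79 the power would be 77.4%.

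**2. Correlations.** Write the cell means as m00 (double placebo), m10 (vitamin D only), m01 (omega-3 only) and m11 (both), each with variance v.
- Interaction I = m11 − m10 − m01 + m00, variance 4v.
- Vitamin D alone: m10 − m00, variance 2v, covariance with I = −2v, correlation −2/√8 = −0.707. Omega-3 alone is the same.
- Combination: m11 − m00, covariance v − v = 0.
- Marginal vitamin D: (m10 + m11 − m00 − m01)/2, covariance 0.

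**3. Error for one agent, no effects.** An agent's claim after a switch is judged by its single-agent contrast. From the bivariate normal with correlation magnitude 0.707, P(flag and single-agent contrast significant) = 0.0169.
- Given a flag: 0.0169 / 0.05 = 34%.
- Overall: 0.95 × 0.05 + 0.0169 = 6.4%.

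The result is still 6.4% for vitamin D if omega-3 has a true effect of 2.3. With no interaction, the same sum gives the coverage of the reported interval: 100 − 6.4 = 93.6%, not 95%.

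**4. Any false claim.** Fixed marginal tests: 1 − 0.95² = 9.75%. Under the rule, at least one of the three comparisons is significant in 57% of flagged null trials (Monte Carlo, 8 million draws): 0.95 × 0.0975 + 0.05 × 0.57 = 12.1%. The rule adds about 2.4 points.

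**5. Power.** A switch takes 529 vs 529 to about 264 vs 264. The standard error grows by √2, so an effect of 2.3 has power Φ(2.80/√2 − 1.96) = 51%, and the difference detectable with 80% power rises to 2.3 × √2 = 3.25. Given a chance switch, simulated power is 50%. Over all trials with an effect of 2.3 and no interaction: 0.95 × 0.80 + 0.05 × 0.50 = 78.5%.

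Steps 2 to 4 need no SD. Step 5 needs only the stated 80% and the halving of the groups.

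**The case against.** The rule was set in advance, no interaction is the stated hypothesis, and the main protocol disclosed the weaker power of the switched comparison. All true, but prespecification does not bring the error back to 5%, and the Addendum's power statement is silent on the switch.

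The plan also declares that it does not correct for multiple comparisons. That does cover most of the 12.1%: 9.75 points come from testing two agents at 0.05 each and would exist without the rule. It does not cover the 6.4%, which arises within one agent's claim.

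The figures depend on what counts as a vitamin D claim after a switch. If the combination arm also counts, the error is 6.6%, but power after a chance switch is then about 75% and average power stays just under 80%. Error and power must be read under one definition; the single-agent definition is used here throughout.

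A switch also protects against averaging unlike effects when the interaction is real. It does so unreliably. The interaction contrast has standard error 2 × 13.35 / √264.5 = 1.64, so a true interaction of 2.3 is flagged in only about 29% of trials, and one of 4.6 is needed for 80%. Reporting the interaction and the cells in every case serves that purpose better.

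A reader might infer that all three switched comparisons are contaminated. They are not: the combination contrast is uncorrelated with the interaction and keeps 5% error after a flag.

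**Conclusion.** The rule does not hold 5% per agent. The excess is about 1.4 points per agent, with an average power loss of at most 1.5 points. This is modest, but it is worth correcting because the correction is cheap and because the problem is concentrated: in a trial that switches by chance, a nominal 5% single-agent test is falsely significant about one time in three.

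Three stronger readings are tempting and not supported. The 34% and 57% are not the trial's false-positive rates; they apply only after a flag, assumed to occur in 1 null trial in 20. The roughly 50% power is likewise not the trial's power. And the alpha in D16 is not a broken promise about the two-stage procedure, since that statement assumes no interaction and describes the marginal test.

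The 5% flag rate is itself an assumption. Time is categorical, so β6 stands for two coefficients, and 15d does not say that year 5 alone counts. If either coefficient could trigger the switch, the flag rate would be about 9% (assuming a correlation of 0.5 between them). A reader might also infer a far higher rate because Equation 1, as printed, has no main effect of time. Equation 2 has one, so this may be a typing omission, and no higher rate is claimed here.

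**What to change.** In 15d, state that the marginal comparison is the primary analysis for each agent whatever the interaction result, and remove the sentence that switches all analyses. Report as secondary results the year-5 interaction estimate with its 95% interval, the four cell means, and the cell comparisons against double placebo, with a note that they are not used to select the primary contrast.

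This restores 5.0% error per agent and keeps the 80% power at 2.3 that D16 claims. It needs SAP wording only, with no change to sample size or conduct. The cost is that under a true interaction the primary estimate is an average over the two levels of the other agent and has to be read alongside the secondary cell results.
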